10.9 Safety Analysis

Safety analyses will include all participants who have received at least one dose of the study medication. The proportion of participants with SAE, AESI and/or AEs leading to treatment discontinuation will be described per study arm and by System Organ Class (using preferred terms defined by MedDRA 13.1), according to the CTCAE, version 5. The proportion of participants presenting at least one AE will be described. Participants with multiple events with the same preferred terms will be counted once. The maximum severity grade for each preferred term and body system will be summarized. If multiple events with the same preferred terms are recorded for a participant, the event with the maximum grade will be

included in the analysis. In addition, a narrative for each of the SAEs and AESI will be developed detailing all aspects related to the medical event. AEs not leading to treatment discontinuation will also be described per study arm using the same classification as presented above.

Incidence rate and 95% confidence interval will be presented per study arm will be presented for SAE and AEs per category and most frequent AEs. Otherwise only descriptive statistics will be presented.

Safety laboratory parameters (hematology and biochemistry) will also be described individually per study arm, showing the proportion of participants by degree of elevation relative to ULN and to baseline values and clinical significance, and blood levels changes over time. Shift tables will be presented. A listing of participants experiencing lab parameters elevation will be included.

EKG abnormalities will be described per treatment arm as the proportion of participants per type of EKG finding, clinical relevance and changes over time. Participants with altered EKG may have an echocardiogram to evaluate cardiac involvement or cardiac progression of CD.

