2.1 Treatment toxicity

The main drawback of BZN and NFX is their high adverse event ratio. The frequency of adverse effects with NFX ranges from 43.0 to 97.5% with the most common being anorexia, weight loss, neurological disorders (irritability, insomnia, disorientation, mood changes, paresthesia, and peripheral neuropathy), digestive manifestations such as nausea and vomiting, and, occasionally, fever and rash. Treatment is discontinued in 14.5–75.0% of cases. (24) For BZN, the most common adverse effects involve hypersensitivity, mainly in the form of skin rash (29–50%), digestive intolerance (5–15%), and general symptoms such as anorexia, asthenia, headache, and sleeping disorders (40%). Neuropathy and depression of bone marrow are considered rare. Treatment is discontinued in 9–29% of cases, even though most reactions are reversible, and severe cases occur in less than 1%. BZN is generally preferred over NFX because of its better tolerability profile. (18)

Since the major limitation of nitroderivative-based therapy is its toxicity, which hampers its efficacy and adherence rates, different approaches have been designed to improve tolerance, mainly based on overall dose reduction. (25)

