6.9.3 Neutropenia

Hematological assessments will be performed as previously described. If Absolute Neutrophil Counts \leq 1000 cells/ μ l are documented, treatment should be discontinued, and CBC will be repeated as soon as possible after the initial abnormality is identified. After that, the participant should be followed every 48 hours (2 days), or the closest possible interval, until the neutrophil counts increase above 1000 cells/mm or stabilize. The event should be immediately reported as an SAE.

In case Absolute Neutrophil Count is found to be $<$ 500 cells/ μ l, the treatment should be immediately interrupted, and a control hematological assessment is required within one day. Participants will be instructed to avoid exposure to people with respiratory tract infections and to respect general hygiene rules. Depending on profile (decreasing phase, stabilization phase, resolution phase), controls will be required every one to three days until normalization. The event should be immediately reported as an SAE.

In case Absolute Neutrophil Count is found to be $<$ 100 cells/ μ l, or below 1000 with associated fever (even of mild intensity) or infectious origin symptoms, the participant should immediately be hospitalized and reported as an SAE.

7. Laboratory assessment

Blood samples for hemogram and biochemistry (5mL each) will be collected in the same day at screening, at days 14 (allowable window of + 2 days), and 56 (allowable window of + 7 days).

Blood samples for serology will be collected at screening visit and at month 24 after EOT.

Blood samples for PCR will be collected at screening visit and at 1, 4, 6, 8, 12, 18 and 24 months after EOT (allowable window of + 10 days. Blood samples collected for PCR shall be immediately added to a tube containing one volume (5mL) of a solution of Guanidine/ClH 6M EDTA 0.2M pH 8,0 Buffer (GEB). Samples

with guanidine buffer can remain at room temperature. Trained nurses will be responsible for the blood collection, sample processing and storage.

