9.13 Rules for permanently interrupting trial treatment

The Investigator will permanently interrupt the treatment based on the following:

- ALT or AST >5x upper limits of normal (ULN) for more than two weeks;
- ALT or AST >3x ULN and Total bilirubin 2x ULN or International Normalized Ratio (INR) >1.5, known as Hy's law criteria, to be reported as a SAE;
- ALT or AST >3x ULN with the appearance of fatigue, nausea, vomiting, right upper quadrant pain or tenderness, fever, rash, and/or eosinophilia (>5%);
- AE or any other condition which, in the investigator's opinion, would put the participant at undue risk by continuing the trial treatment;
- Major protocol deviation incompatible with the continuation/participation on the trial;
- Any condition that the investigators consider medically necessary to interrupt the treatment, such as:
 - Significant leukopenia (<500 cells/mm³);
 - Severe gastrointestinal symptoms;
 - Severe allergic dermatopathy;
 - Peripheral sensitive neuropathy.
- Pregnancy.

Regardless of the reasons for trial treatment interruption, the investigator will make all necessary arrangements to ensure that the participant receives the appropriate treatment for the relevant medical condition. Rescue treatment will be offered for these participants, if appropriate, upon trial completion.

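### Section 10.9 grades and lists hematology results by elevation only, so falls in blood counts have no category in either output (minor)

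*Protocol*

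**What the plan says.** Protocol section 10.9 covers both laboratory panels at once: "Safety laboratory parameters (hematology and biochemistry) will also be described individually per study arm". The sentence then fixes the categorical summary, "showing the proportion of participants by degree of elevation relative to ULN and to baseline values and clinical significance", and adds "and blood levels changes over time". Two further outputs follow: "Shift tables will be presented", and "A listing of participants experiencing lab parameters elevation will be included". No lower limit of normal and no low-value category is named.

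Elsewhere the protocol treats falls as the hematological hazard. Section 2.1, on benznidazole, says "Neuropathy and depression of bone marrow are considered rare". Section 6.9.3 provides that at a neutrophil count of 1000 cells/µl or less "treatment should be discontinued, and CBC will be repeated as soon as possible after the initial abnormality is identified", with further steps below 500 and below 100, and requires SAE reporting. Section 9.13 gives "Significant leukopenia", below 500 cells/mm³, as an example of a condition for permanent interruption.

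**The concern.** A summary by degree of elevation is the natural display for transaminases and renal markers. Applied to blood counts it looks the wrong way: a raised leukocyte count is graded and listed, while a reduced one is neither.

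The secondary objective in section 3 is the safety profile of 2 and 4 weeks against 8 weeks. If longer exposure produces more mild cytopenia, the graded laboratory table and the participant listing are where a reader would look first. As worded, neither can show it in any arm.

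**Working it through.** No figure in the protocol is at issue, so the check sets the texts side by side.

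**Which outputs in 10.9 can show a fall?**

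1. Proportion by degree: elevation only. The reference to baseline does not help, because it also qualifies elevation. Falls have no category.
2. Participant listing: elevation only. Falls are left out.
3. Changes over time: no direction stated. Falls are covered in aggregate.
4. Shift tables: no direction stated. Normal-to-low movement can be shown, although 10.9 defines no categories for these tables.

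**Which counts are concerned?** Section 8.1 lists hemoglobin, leukocytes with differential, and platelets at screening. On treatment the platelet data are less certain: section 7 speaks of a hemogram, while the hematology footnote to the schedule in section 12 names only red and white cells.

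**Which falls reach the reader by another route?**

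- Neutrophils at or below 1000: reported as SAEs under 6.9.3, so tabulated by arm and given a narrative under 10.9.
- Clinically significant falls that stop the drug: AEs under 9.1, and tabulated under 10.9 as AEs leading to discontinuation.
- Other falls: AEs only if judged clinically significant and if at least one of the three conditions in 9.1 is met. Section 9.5 also ties CRF reporting of AEs to being considered treatment related.
- The remainder, for example a neutrophil count of 1,200 that is not recorded as an AE: absent from the graded summary and the listing, and visible only through shift tables and changes over time. This assumes that 1,200 lies below the laboratory's lower limit, which the protocol does not state.

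**Which samples matter?** Sections 7 and 12 schedule hematology during the treatment period at days 14 and 56. Under 6.1 all arms receive active drug for the first two weeks, so planned exposure is the same at day 14. By day 56 the 4-week arm has had 56 − 28 = 28 days of placebo and the 2-week arm 56 − 14 = 42 days, while the 8-week arm is completing active treatment. A duration effect in scheduled hematology can therefore appear only at day 56: one sample per participant, at most 672 in all, or 224 per arm. The protocol gives no rate of mild cytopenia, so the number of falls affected cannot be estimated.

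**The case against.** The strongest reply is that little is lost. The falls on which the protocol acts are the best captured elsewhere, through SAE reports, narratives and the tables of AEs leading to discontinuation. Milder falls can enter the AE tables, which summarise maximum severity by preferred term with CTCAE grading under 9.7; the worked example in 9.1 is itself a fall, anemia. Shift tables and changes over time can show the rest. The outputs in question are descriptive, and section 2.1 calls marrow depression rare. The direction of display for each analyte is commonly settled in a statistical analysis plan, which is not shown here.

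Most of this stands, and it sets the severity. Two parts do not. First, the protocol is not silent: it names the metric, the reference and the content of the listing, and applies them expressly to hematology, so an analysis plan that follows it inherits the wrong direction. Second, the AE route depends on investigator judgement, whereas a graded laboratory summary is meant to be independent of that judgement; shift tables do not replace a participant-level listing.

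A reader might infer that 10.9 hides marrow toxicity altogether, or that the safety comparison fails. The routes above rule that out, and the powered safety comparison in 10.1 concerns treatment interruption. A reader might also take the stopping rules to act on platelets and hemoglobin. They do not: the count rules in 6.9.3 and 9.13 concern neutrophils and leukocytes, and the rules on raised transaminases are matched by the present wording. Nor is the summary confined to values above the ULN, since elevation relative to baseline is counted as well.

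**Conclusion.** The point holds as a minor reporting defect. In two descriptive laboratory outputs, the proportion by degree and the participant listing, an elevation-only rule is applied to hematology, and falls in blood counts have no category in either. This includes the low neutrophil and leukocyte counts on which 6.9.3 and 9.13 act, though those should surface through SAE and AE reporting. The practical gap is mainly milder falls not recorded as AEs. The primary efficacy analysis, the discontinuation endpoint and SAE reporting are unaffected.

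The conclusion rests on reading 10.9 as written, with elevation governing hematology as well as biochemistry, and on the assumption that no unseen analysis plan already corrects the direction.

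**What to change.** Reword 10.9 as follows.

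- Biochemistry (ALT, AST, urea, creatinine): keep the proportion by degree of elevation relative to the ULN and to baseline.
- Hematology (hemoglobin, leukocytes, neutrophils, and platelets where measured): report the proportion by degree of decrease relative to the lower limit of normal and to baseline, using the CTCAE v5.0 grades adopted in 9.7. Keep eosinophil elevation, since 9.13 refers to it.
- Listing: include participants with any value outside the normal range in the direction of toxicity.

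While doing so, state whether platelets are part of on-treatment hematology, so that sections 7 and 12 agree.

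The cost is one more table and a longer listing from data already collected. Clinical rules, visits and samples stay as they are. Making the change before any unblinded look at the data avoids a later choice of cytopenia tables made with the results in view.

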10.10 Exploratory objectives Analysis

Exploratory objectives are to evaluate the incidence and severity of clinically relevant events attributed to CD, measure the QoL of participants, and to assess the cost-effectiveness of two regimens, among participants with chronic CD.

Incidence and severity of clinically relevant events attributed to CD

For the first objective a composite clinical endpoint will be defined considering the more relevant clinical events related with the cardiac progression of CD, such as death, resuscitated cardiac arrest, insertion of a pacemaker or an implantable cardioverter-defibrillator, sustained ventricular tachycardia, cardiac transplantation, new heart failure, stroke or transient ischemic attack. Results will be expressed as proportion of participants in each arm and a comparison between them. Moreover, EKG abnormalities will be described per treatment arm as the proportion of participants per type of EKG finding, clinical relevance and changes over time. Echocardiography will be performed at baseline, annually or when new abnormalities on the EKG appear during follow-up period.

Quality of life (QoL)

For the QoL objective, validated questionnaires will be completed by participants during each visit. The WHOQOL Bref will be completed during the baseline visit and at the end of follow up, and the EQ-5D-3L questionnaire will be completed during all visits. Questionnaires must be completed BEFORE any procedures of the proposed visit and must be self-applied. Only a person not related to the research can help the participant during the completion. Longitudinal differences on quality-of-life scores between groups will be fitted using linear mixed models.

EQ-5D-3L questionnaires will be completed to allow the estimation of health utilities (a value between 0 and 1 estimated using country-specific value sets; 0 represents death and 1 full health). The health utilities will be used to calculate quality-adjusted life-years (QALYs) gained. We need EQ-5D-3L to estimate the health utility of each health state within the course of Chagas disease (e.g. cardiomyopathy form, gastrointestinal form, among others). This will be a parameter for our economic analyses. Unfortunately,

EQ-5D is short and includes only 5 dimensions. These questionnaires should preferably be self-administered, but whenever this is not possible, the questionnaire could be read out loud by the interviewer. It is expected to take an average of 5 minutes to fulfill all the items.

WHOQOL Bref has the advantage of being more generic, including more dimensions. It will be very useful as a secondary outcome for the clinical trial. However, it cannot be used to obtain health utilities for cost-effectiveness studies. Additionally, it would be possible to compare and crosswalk the two questionnaires considering the specific study visits when both measures will be completed.

The WHOQOL-BREF should be self-administered if respondents have sufficient ability. If this is not possible, interviewer-assisted or interview-administered forms should be used. Standardized instructions, which are provided on the second page of the WHOQOL-BREF example assessment, should be read out to respondents in instances where the assessment is interviewer-administered. It is expected to take an average of 15 minutes to fulfill all the items.

We have decided to include both measures to estimate impacts on several dimensions of the interventions studied and to generate parameters for our cost-effectiveness study.

Both WHOQOL-BREF and EQ-5D-3L questionnaires have been adapted for each country. For the WHOQOL-BREF are available two versions, Colombian and Chilean, which will be used in Bolivia. For the EQ-5D-3L questionnaires only one available version, the Colombian, which will be used in Colombia and Bolivia.

Cost-effectiveness Analyses

An economic evaluation alongside the primary clinical trial will be conducted following the International Society for Pharmacoeconomics and Outcomes Research, Inc (ISPOR) recommendations. The use of all types of resources within the clinical trial will be collected prospectively at the participant-level to assess the individual direct and indirect costs through study forms and electronic medical records. The collected protocol-driven resource use will be reviewed to allow estimation to reflect the future real-world resource use. Individual participant-level data regarding units of resources (e.g. medical visits, diagnostic tests, drugs, hospitalization) will also include all the procedures associated with the management of AE. There will be an effort to include medical and non-medical resources (e.g. transportation, absence from work). The full list of resource units will be pilot tested in each study site to investigate the feasibility.

A valuation procedure will be conducted to provide country-specific data that will be assigned for all unit costs. The imputation of available information from the most similar setting will be considered should country-specific data not be available.

The obtainment of the number of units used per-participant and the value of each unit will allow the inclusion of costs incurred at participant-level in the database for the study interventions.

Incremental cost-effectiveness ratios (ICER) will be obtained by dividing the incremental cost by the incremental health benefit. This means that the ICER will be calculated using the costs of reduced BZN treatment minus the cost of the standard treatment for chronic CD as numerator, and the effectiveness of reduced BZN treatment minus the effectiveness of the standard treatment as denominator.

The outcome of the cost-effectiveness study will be the cost per QALY gained. The QALYs will be obtained after the multiplication of years lived after each intervention by the utility values of each health state lived within the study duration.

10.11 Joint analyses of NuestroBen and Benlatino trials

For that purpose we have considered the following aspects.

In the NuestroBen trial in Argentina, each of three arms (durations of 60, 30, and 15 days) will enroll 100 participants. In the BENLatino study, 112 patients will be available per country (Bolivia and Colombia) and per arm (60, 30, and 15 days), resulting in 672 total patients. The studies will share overall efficacy results (proportions of patients with sustained clearance at 12 months follow-up) to utilize a dynamic borrowing approach in the analysis, described below.

The primary endpoint is negative serial qualitative PCR results from the end of treatment with the elimination of sustained parasitaemia until the end of 12 months' follow-up from the beginning of treatment. The primary analysis tests whether either of the 30 or 15 day arms is noninferior to the 60 day arm, using a noninferiority margin of 20%. The trials have been powered based on an assumed 80% efficacy/20% failure rate in the 60 day arm. Let p_{60} , p_{30} , and p_{15} be the response rates in each arm. Specifically, we are testing the hypotheses

$$H_0 : p_{60} \geq p_d + 0.20 \text{ for } d=30 \text{ and } 15$$

$$H_1 : p_{60} < p_d + 0.20 \text{ for either } d=30 \text{ or } d=15.$$

The primary analysis is a Bayesian test that declares noninferiority if the posterior probability of noninferiority for either arm (either $\Pr(p_{60} < p_{30} + 0.20)$ or $\Pr(p_{60} < p_{15} + 0.20)$) exceeds 0.9875.

We calculate both posterior probabilities of noninferiority using a model that incorporates both the data from the NuestroBen trial (300 participants) and the BENLatino trial data (anticipated 672 participants). Let p_{60b} , p_{30b} , and p_{15b} be the response rates for the BENLatino Bolivia patients, and p_{60c} , p_{30c} , and p_{15c} be the response rates for the BENLatino Colombia data. Where needed, we will use p_{60a} , p_{30a} , and p_{15a} interchangeably with p_{60} , p_{30} , and p_{15} to emphasize we are referring to the Argentina parameters.

Within each arm and country, we assume response rates are Binomial. If Y_{dr} is the number of responses within duration d ($d=60,30,15$) in region r ($r=a,b,c$ for Argentina, Bolivia, and Colombia) and n_{dr} is the total number of participants in that duration and region, then

$$Y_{dr} \sim \text{Bin}(n_{dr}, p_{dr})$$

We place a hierarchical model on the 9 arm/country response rates to combine information across countries (no borrowing is conducted across arms). For each d and r let

$$\theta_{dr} = \log \frac{p_{dr}}{1 - p_{dr}}$$

Indicating the logit of the corresponding rate.

We first place independent noninformative priors on the response rates in each country for the 60 day duration.

$$\theta_{60a}, \theta_{60b}, \theta_{60c} \sim N(0, 10)$$

We then define treatment effects δ_{30r} and δ_{15r} relating the 30 and 15 day durations to the 60 day duration.

$$\theta_{30r} = \theta_{60r} + \delta_{30r}$$

$$\theta_{15r} = \theta_{60r} + \delta_{15r}$$

The treatment effects are then placed in hierarchical model, borrowing information across countries (but not across durations)

$$\delta_{30a}, \delta_{30b}, \delta_{30c} \sim N(\eta_{30}, \tau_{30})$$

$$\delta_{15a}, \delta_{15b}, \delta_{15c} \sim N(\eta_{15}, \tau_{15})$$

with hyperpriors

$$\eta_{30}, \eta_{15} \sim N(0, 10)$$

$$\tau_{30}^2, \tau_{15}^2 \sim IGamma(\text{center} = 0.3, \text{weight} = 0.5)$$

This prior creates dynamic borrowing across the three countries. If the observed treatment effects appear similar across the three countries, the model borrows strength between the countries and obtains more precise treatment effect estimates. If the observed treatment effects are different, then less borrowing is performed and the data from each country will stand more on its own. This hierarchical borrowing methodology improves power and reduces type 1 error when the countries are qualitatively similar (exact equality is unnecessary) in terms of treatment effects, while presenting risks of decreased power and inflated type 1 error if one country differs significantly from the others. Given the apriori belief that the countries are more likely to be similar than they are to be different, the benefits of borrowing are viewed to exceed the risks.

After obtaining data, the posterior distribution of all parameters can be obtained, particularly the posterior distributions of p_{60} , p_{30} , and p_{15} . These will allow the calculation of the posterior probabilities of noninferiority. An arm will be declared to be noninferior if $\Pr(p_{60} < p_{30} + 0.20)$ or $\Pr(p_{60} < p_{15} + 0.20)$ exceeds 0.9875.

11. Quality assurance and quality control procedures

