In this international, multicenter, double-blind, phase III, placebo-controlled study, 672 participants will be randomly assigned to receive the standard-dose of benznidazole (300 mg daily for 8 weeks) or the short experimental regimens (benznidazole 300 mg daily for the first 2 weeks plus placebo for the last 6 weeks or benznidazole 300 mg daily for the first 4 weeks plus placebo for the last 4 weeks). Efficacy will be assessed considering a non-inferiority design and through the detection of parasite deoxyribonucleic acid (DNA) through molecular biology (Polymerase Chain Reaction - PCR). Meanwhile, safety will be evaluated through a superiority design, with the aim to find the new regimen as effective as the standard one, but superior in terms of safety. An intention-to-treat analysis will be performed, and statistical significance will be set at 0.025 for the non-inferiority outcome (positive PCR) and 0.05 for the superiority outcome.

The study population will be adult participants, 18 years or older, with chronic Chagas disease in its indeterminate or mild cardiac forms, with a positive diagnosis from two serological assays. The trial will be conducted in four sites: two in Bolivia, and two in Colombia. The primary endpoint will be parasitological response determined as sustained negative qualitative PCR at 24 months after treatment. The proportion of participants with positive qualitative PCR will be measured at 1, 4, 6, 8, 12, 18, and 24 months from end of treatment. The frequency of adverse events leading to treatment discontinuation will be compared. An economic evaluation will be conducted assessing the direct and indirect costs, including procedures associated with the management of adverse events.

Key words

Chagas disease, treatment, short regimen, benznidazole.

1. Rationale and background information

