10.1 Sample Size Determination

A total sample size of 672 subjects (224 per trial arm, and 336 per country) will be necessary to achieve 90% power to detect a non-inferiority margin difference of 15%, assuming that the standard regimen failure rate is 10% and the intervention regimen is 12%, for a one-sided Z test at a significance level of 0.025. This total sample size has been increased in anticipation in 40% to assure a minimum 60% of participants with active infection (positive PCR) and further by 10% to account for potential losses to follow-up, in order to maintain the specified power and inferiority/superiority margins. This means that individuals removed from the study for the reasons mentioned will not be replaced. This sample size will allow the study to also demonstrate a superiority margin of difference of 10% with 80% power regarding the safety of the experimental arm. Considering the percentage of treatment interruption for conventional treatment of 20%, and a reduction of 50% in the experimental arm, power of 90% and $\alpha=0.05$, 197 patients will be needed in each arm.

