A control event rate is expected to be 10% of treatment failure (at least one positive PCR during follow up period) and a 20% of treatment withdrawn due to any AE. Control arm showing posterior probability of superiority of 97.5% or higher will be considered superior. This will be calculated for the experimental intervention versus the control group based on the observed data at the time of interim assessment with a superiority p-value stopping boundary of 0.010.

The decision for interim analysis will be made in a blinded manner (e.g., based on pooled number of events).

All analyses will be performed using Stata 13.0 for Windows.

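### Section 10.11 attributes a 20% control failure rate to BENLATINO's powering, against 10% in 10.1 and 10.3, and gives a 12-month, 20-point rule the label primary without saying for which trial or how it ranks

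*Protocol*

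**What the plan says.** **Powering.** Section 10.1 derives 224 per arm (672 in total) from 90% power, a 15-point margin and a one-sided 0.025 test, "assuming that the standard regimen failure rate is 10% and the intervention regimen is 12" per cent. It then adds allowances so that 60% PCR-positive participants suffice and for 10% losses. Section 10.3 repeats the control rate: "A control event rate is expected to be 10% of treatment failure", with failure meaning at least one positive PCR during follow-up. Section 10.11 introduces NuestroBen (100 per arm) and BENLATINO (672 in total) and then states: "The trials have been powered based on an assumed 80% efficacy/20% failure rate in the 60 day arm".

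**Primary endpoint and rule.** The Abstract says: "The primary endpoint will be parasitological response determined as sustained negative qualitative PCR at 24 months after treatment". Sections 3, 10.3 and 10.8 agree on 24 months, and 10.4 sets the margin at 15 points for this study. Section 10.11 begins its definition "The primary endpoint is negative serial qualitative PCR results from the end of treatment" and runs it to 12 months from the start of treatment. It describes its primary analysis as "using a noninferiority margin of 20" per cent, with a posterior probability threshold of 0.9875. Its closing decision rule starts "An arm will be declared to be noninferior if". The only sign of ownership is notational: the unsubscripted response rates are used interchangeably with the Argentina ones, "to emphasize we are referring to the Argentina parameters".

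**The concern.** A single protocol gives BENLATINO two control failure rates as the basis of its size. Someone checking the sample size from 10.11 would use a rate that 10.1 does not use.

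The same section also puts a second endpoint and analysis, both called primary, into BENLATINO's protocol, with a wider margin and an earlier time point. A true deficit between 15 and 20 points is inferior under BENLATINO's margin and noninferior under the other. If the joint analysis reports first and declares an arm noninferior, the protocol should already say whether that statement carries BENLATINO's conclusion.

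**Working it through.** **Inputs.** From 10.1: failure 10%/12%, margin 15 points, one-sided 0.025, 90% power, 60% PCR-positive, 10% loss. From 10.11: control failure 20%. Section 10.11 gives no short-arm rate, so 20% (no difference) and 22% (the 2-point difference of 10.1 carried over) are assumptions.

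**Formula.** Evaluable n per arm = (z_alpha + z_beta)² × [pc(1−pc) + pe(1−pe)] / (margin − (pe − pc))², with failure rates and unpooled variance. Enrolled = n / (0.6 × 0.9) = n / 0.54.

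**1. The plan's own figure.**
- (1.960 + 1.282)² × (0.09 + 0.1056) / 0.13² = 121.6 evaluable.
- 121.6/0.6 × 1.1 = 223.0; 121/0.54 = 224.1; 122/0.54 = 225.9; 121/0.6 × 1.1 = 221.8. Depending on rounding this is about 222 to 226, against 224 stated.

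**2. The 20% rate in BENLATINO's design (15 points, 0.025, 90%).**
- 20%/20%: (3.242)² × 0.32 / 0.15² = 149.4 evaluable; /0.54 = about 277 enrolled.
- 20%/22%: (3.242)² × (0.16 + 0.1716) / 0.13² = 206.2 evaluable; /0.54 = about 382 enrolled.

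**3. Sensitivity to the allowance.** Section 10.1 words the first allowance as a 40% increase. Taken literally, 10%/12% gives 121.6 × 1.4 × 1.1 = 187 and does not reach 224. Adding the two percentages (factor 1.5) gives 149.4 × 1.5 = 224.1 at 20%/20% and 121.6 × 1.5 = 182 at 10%/12%. Division by 0.6 is the reading that leaves enough participants when only 60% are PCR-positive, and it is the one that matches the rates 10.1 states. The arithmetic therefore supports 10.1 on that reading but is not unique.

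**4. Power of the 15-point test.** Power = Φ((margin − difference)/SE − 1.960). Planned evaluable per arm: 224 × 0.54 = 121.

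| Failure, control/short arm | n per arm | Power |
|---|---|---|
| 10%/12% | 121 | 89.9% |
| 20%/20% | 121 | 83.1% |
| 20%/22% | 121 | 70.0% |
| 20%/22% | 224 (all randomised) | 92.2% |

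**5. Does 20% fit NuestroBen?** With 20%/20%, 20 points, one-sided 0.0125 and 90% power, n = 99.3, close to its 100 per arm. The power, the short-arm rate and the use of 0.0125 as a stand-in for the 0.9875 threshold (no borrowing) are assumptions, so this is a plausibility check only.

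**6. Can the time points reconcile 10% and 20%?** No. Failure in 10.3 is cumulative, so failure by 12 months should not exceed failure by 24 months. Yet 10.11 has the higher rate at the earlier time.

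**The case against.** **Ownership is indicated.** The hypotheses and the decision rule in 10.11 are written in symbols equated with Argentina's parameters, and Bolivia and Colombia enter as borrowed data. The section is headed as a joint analysis. This stands: the rule is most likely NuestroBen's. What is missing is a statement in prose and a rank for BENLATINO.

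**The primary is settled elsewhere.** A reader might infer that 10.11 replaces or loosens BENLATINO's primary test. The protocol does not support that: the Abstract and sections 3, 10.3, 10.4 and 10.8 fix 24 months and 15 points between them, and 10.11 proposes no 20-point test on pooled BENLATINO counts. A statistical analysis plan could settle the rank, but it would not remove the unqualified label from the protocol.

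**The trial is not shown to be underpowered.** A reader might infer this from 70.0%. That figure combines 10.11's control rate with 10.1's margin, uses an assumed short-arm rate and counts only PCR-positive evaluable participants. With 10.11's own margin and a one-sided 0.0125 test, 121 per arm gives 95.0% at 20%/20% and 88.4% at 20%/22%. On all 224, which is the intention-to-treat set of 10.3, the 15-point test has 92.2% at 20%/22%. This objection stands in full.

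**224 can be reached from 20%.** With additive allowances and 20%/20% it can. That does not reconcile the text, because 10.1 states 10% and 12% in words. If the number did come from 20%, then 10.1 and 10.3 would be the sections to correct.

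**Conclusion.** The inconsistency is real. As 10.1 and 10.3 describe BENLATINO, the 20% powering sentence is wrong for it. The stated 224 follows from 10%/12% when the PCR allowance is division by 0.6; 20% then needs about 277 to 382, given short-arm rates of 20% to 22%. If control failure were 20%, the 15-point test on about 121 evaluable per arm would have 83.1% to 70.0% power instead of 89.9%. This measures how much the two assumptions differ; it does not show that the trial is too small.

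The second part is a labelling gap. A 12-month, 20-point rule is called primary, its owner is given only by notation, and it has no rank against the 24-month, 15-point primary. BENLATINO's own primary is not in doubt. NuestroBen's protocol is not at hand, so attributing the rule and the 20% to it is an inference. The point should be fixed because the misstatement can be verified and correcting it costs little.

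**What to change.** In section 10.11:

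1. Correct the powering sentence so that 20% is not attributed to BENLATINO. State 10%/12% for BENLATINO as in 10.1, and keep 20% for NuestroBen if that is its assumption. The sponsor should confirm the derivation of 224 while doing so.
2. State which trial the 12-month, 20-point primary endpoint and analysis belong to (NuestroBen, if so), and that the joint analysis is not primary for BENLATINO.
3. Add that BENLATINO's own noninferiority conclusion rests on its 24-month, 15-point test.

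The cost is a few sentences. Provided 10.1 is confirmed, sample size, visits, the joint model and BENLATINO's primary analysis do not change.
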